#### 6.1.1 Definitions

Evaluable for toxicity. All subjects will be evaluable for toxicity from the time of their registration.

Evaluable for objective response. Only those subjects who have undergone SABR and one course of HD IL-2, and have had their disease re-evaluated at least at two occasions (8wk and 16wk) will be considered evaluable for response. These subjects will have their response classified according to the definitions stated below.

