## STUDY SCHEMA

## STUDY SUMMARY

Title	A Phase II Trial of High Dose IL-2 and Stereotactic Ablative Body Radiation Therapy (SABR) for Patients with Metastatic Clear Cell Renal Cell Cancer (mRCC)		
Short Title	HD IL-2 and SABR for metastatic RCC		
Protocol Number	STU 012013-041		
Phase	Phase 2		
Methodology	Single Arm, open label.		
Study Duration	Six years (two years for enrollment and 4 years for follow-up).		
Study Center(s)	Single-center		
Objectives	To evaluate the improvement in response rate (RR) and complete response (CR) of mRCC after treatment with SABR and HD IL-2		
Number of Subjects	Average 33; maximum 38		
Diagnosis and Main Inclusion Criteria	Metastatic Clear Cell Renal Cell Carcinoma		
Study Product(s), Dose, Route, Regimen	HD IL-2 (brand name Proleukin), 600,000 U/kg q8h X 14 dose, IV infusion; SABR dose varying from 8Gy-20Gy in 1-3 fractions.		
Duration of administration	HD IL-2: 1 weeks/cycle; maximum of 2 cycles/course over three weeks; Maximum of three courses. SABR: 1-3 fractions over one week.		
Reference therapy	HD IL-2		

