## 2.4 Endpoints

- **2.4.1 Response:** Treatment response will be measured using the immune related RECIST criteria (iRECIST) which are a minor modification of RECIST 1.1 for immunotherapy [91].
- **2.4.2 Death:** Death due to any cause, although in mRCC patient population, the overwhelming majority is expected to be secondary to disease progression.
- **2.4.3 Progression:** Progression will be defined according to the iRECIST criteria and verified by a second set of imaging at least 6 weeks apart.
- **2.4.4 Immune Response:** Immune response will be measured using ELISpot assay, T-cell proliferation assay and ELISA.
- 2.4.5 Toxicity: Toxicity will be measured using CTAE v4.0
- **2.4.6 HRQoL**: HRQoL will be measured using FACT-G, EQ-5D and FKSI questionnaire at baseline, after HD IL-2, and at four-month intervals after treatment.
- 2.4.7 **Cost-effectiveness analysis**: Health care utilization data needed to assess costs will be obtained from treatment records to include costs of hospitalization, treatment, ER visits, physician and clinic visits and medications. Markov modeling with probabilistic sensitivity analysis will be used to correlate quality-adjusted survival and cost.

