## 4.2.1 Treatment Dosage and Administration

HD IL-2 will be administered at a dose of 600,000 IU/kg every 8h for a total of up to 14 doses (considered as one cycle), followed by a one week break and then another cycle of the same dose over another week. Each HD IL2 course consists of two cycles of up to 14 doses each separated by a week of rest. A total of three courses may be administered for patients without progression at the discretion of the medical oncologist. Patients will be admitted to the ICU of the corresponding hospital for IL-2 treatment and close monitoring according to the HD IL-2 algorithm (appendix B). Patients will undergo placement of a central venous catheter, typically a PICC line, before each course of therapy.

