#### 4.4 Duration of Follow Up

Subjects will be followed for ten years or death (although findings will be analyzed and reported at a median follow up of 2-4 years), whichever occurs first. Subjects removed from treatment for unacceptable adverse events will be followed until resolution or stabilization of the adverse event. The follow-up will be every 8 weeks (+/- 2 Weeks) from study registration with imaging studies and physical exam every 8 weeks for the first eight months, then every 12 weeks (+/- 2 Weeks) until two years, then every four months thereafter for a total of five years, and then every six months (+/- 1 month) for a total of ten years. See section 5.0 for detail.

Subjects who show progressive disease will be followed for survival and will no longer strictly adhere to study calendar. QOL questionnaires will be completed every 4 months until 1 year after treatment.

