## 4.5 Removal of Subjects from Protocol Therapy

Subjects will be removed from therapy when any of the criteria listed in Section 5.5 apply, however will continue to be followed up as per protocol described above. Notify the Principal Investigator, and document the reason for study removal and the date the subject was removed in the Case Report Form.

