## 5.5 Removal of Subjects from Study

Subjects can be taken off the study treatment and/or study at any time at their own request, or they may be withdrawn at the discretion of the investigator for safety, behavioral or administrative reasons. The reason(s) for discontinuation will be documented and may include:

- 5.5.1 Subject voluntarily withdraws from treatment (follow-up permitted);
- 5.5.2 Subject withdraws consent (termination of treatment and follow-up);

5.5.3 Subject is unable to comply with protocol requirements; patients must be withdrawn from the trial and replaced if they failed to receive at least one cycle of HD IL-2

- 5.5.4 Subject demonstrates disease progression (unless continued treatment with HD IL-2 is deemed appropriate at the discretion of the medical oncologist);
- 5.5.5 Subject experiences toxicity that makes continuation in the protocol unsafe;
- 5.5.6 Treating physician judges continuation on the study would not be in the subject's best interest;
- 5.5.7 Subject becomes pregnant (pregnancy to be reported along same timelines as a serious adverse event);
- 5.5.8 Development of second malignancy (except for basal cell carcinoma or squamous cell carcinoma of the skin) that requires treatment, which would interfere with this study;
- 5.5.9 Lost to follow-up.

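### The primary response rate has no stated all-treated denominator: response is classified only in an evaluable subset, and nobody outside it is counted as a non-responder

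*Combined protocol and SAP*

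**What the plan says.** Section 6.1.1 defines two sets. Every registered subject is evaluable for toxicity. For response the set is narrower: "Only those subjects who have undergone SABR and one course of HD IL-2", with a scan requirement added: "have had their disease re-evaluated at least at two occasions (8wk and 16wk) will be considered evaluable for response". Response is then classified for these subjects.

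A course is two cycles. Section 4.2.1 says "Each HD IL2 course consists of two cycles of up to 14 doses each separated by a week of rest", and sections 4.3 and 5.2 agree.

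Section 6.1.5 defines RR as CR plus PR and gives no denominator. Section 11.2 sets the decision rule: stop at 3 or fewer responses in 17, and go forward with more than 9 in 33, against rates of 23% and 36.8%. Section 11.3 calls for an exact binomial estimate and interval but names no analysis set.

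The one replacement rule is in section 5.5.3: "patients must be withdrawn from the trial and replaced if they failed to receive at least one cycle of HD IL-2".

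Two provisions limit how many patients fall outside the evaluable set. Progression must be "verified by a second set of imaging at least 6 weeks apart" (section 2.4.3), and section 4.4 says "The follow-up will be every 8 weeks (+/- 2 Weeks) from study registration". The notes to section 6.1.4.3 give symptomatic deterioration its own label and ask for continued efforts to document progression.

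**The concern.** RR is the primary endpoint and is compared with a historical 23%. The conditions for being evaluable are met after treatment starts and depend on how the patient fares. A patient who dies early, stops IL-2 for toxicity during the first course, drops out, misses the week-8 or week-16 scan, or deteriorates without documented progression is outside the set. So is a patient who progresses before week 16 by cord compression, or by a fracture at a site not treated with SABR, if the second re-evaluation is never done; those events need no confirmatory scan. No text says how any of these patients count.

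If they are left out and respond less often than the rest, the reported RR is too high. If they respond equally often, there is no bias. Where excluded patients are also replaced, the chance of a false go decision changes as well.

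**Working it through.** **1. The plan's own design.** Inputs from section 11.2: r1/n1 = 3/17, r/n = 9/33, p0 = 0.23, p1 = 0.368. With X1 ~ Bin(17, p) and X2 ~ Bin(16, p):

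- P(early stop) = P(X1 ≤ 3)
- P(go) = Σ over x = 4,…,17 of P(X1 = x) × P(X2 ≥ 10 − x)
- Expected N = 17 + 16 × [1 − P(early stop)]

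At p = 0.23: early stop 0.427, go 0.197, expected N = 17 + 16 × 0.5728 = 26.2. At p = 0.368: go 0.805. These reproduce the plan's 0.43 and 26.2 and meet its 0.20/0.20 limits. The design arithmetic is right; the gap is in who is counted.

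**2. Who the two-scan condition loses.** Progression seen at week 8 is rescanned at least 6 weeks later, so from about week 8 + 6 = 14. The week-16 visit window is 14 to 18 (16 ± 2). Most scan-defined progression should therefore reach a second re-evaluation and be classified. The remaining gap is the list given under the concern.

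**3. Reported RR.** Suppose 9 responses among 33 treated, with 2 or 5 non-responders left out (assumed counts). Exact 95% intervals:

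- 9/33 = 27.3% (13.3–45.5)
- 9/31 = 29.0% (14.2–48.0)
- 9/28 = 32.1% (15.9–52.4)

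Nine responses is a no-go in each case. The example shows reporting bias, not a changed decision.

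**4. Go/no-go error.** If non-evaluable patients stay among the 33 with no response, the rule is applied to the all-treated rate and the error at 23% is 0.197, whatever their number.

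Under section 5.5.3, let a fraction f be replaced and let those patients respond at k times the overall rate p. The rate among those counted is p(1 − fk)/(1 − f). At p = 0.23:

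| f | k = 0: counted rate | false go | early stop | k = 0.5: counted rate | false go |
|---|---|---|---|---|---|
| 2% | 0.2347 | 0.215 | 0.409 | 0.2323 | 0.206 |
| 3% | 0.2371 | 0.225 | 0.400 | 0.2336 | 0.211 |
| 5% | 0.2421 | 0.246 | 0.381 | 0.2361 | 0.221 |

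At p = 0.20, the lower end of the historical range in section 1.4, with k = 0, false go is 0.110, 0.116 and 0.129. All are below 0.20.

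**5. Price of an all-treated denominator.** If 23% and 36.8% both describe evaluable patients, and a fraction d is non-evaluable and never responds, both rates shrink by (1 − d):

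| d | 0.23(1 − d) | false go | 0.368(1 − d) | power |
|---|---|---|---|---|
| 2% | 0.2254 | 0.179 | 0.3606 | 0.781 |
| 5% | 0.2185 | 0.155 | 0.3496 | 0.742 |
| 10% | 0.2070 | 0.118 | 0.3312 | 0.668 |

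The documents give none of f, k or d. All are assumptions.

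**The case against.** The strongest reply is that section 11.2 counts responses against fixed totals of 17 and 33 and never says those totals are evaluable patients. A patient with one cycle and a missed scan could stay among the 33 without a response, and the error would then be 0.197. This stands as a possible reading. No text states it, however, and section 6.1.1, the only definition of who has response classified, points the other way.

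A second reply is that the denominator behind 23% is not in the documents. If it is an evaluable-patient rate, an evaluable-set RR compares like with like, and an all-treated RR costs power. That also stands. It is a reason to state the denominator and report both rates, not to leave the matter open.

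Four stronger readings are tempting but unsupported:

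- **The false-go rate is 0.306 or more.** That needs 10% non-evaluable, none responding and all replaced. Only patients with less than one cycle are to be replaced. The Study Summary's maximum of 38 differs from 33 in section 11.2, but nothing links the extra 5 to replacement.
- **Early progressors as a group drop out.** The confirmation scan keeps most of them in.
- **The meaning of a course is unclear.** The Study Summary's "maximum of 2 cycles/course over three weeks" is loose, but sections 4.2.1, 4.3 and 5.2 all make a course two cycles.
- **OS and PFS data are lost.** Section 5.5.3 speaks of withdrawal from the trial, but section 4.5 says that subjects removed under section 5.5 "however will continue to be followed up as per protocol described above". A cross-reference is enough.

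**Conclusion.** The point holds and should be fixed. As written, response is classified only in a set selected after treatment starts, no other denominator is named for the primary RR, and no rule counts the remaining patients as non-responders. That the evaluable set is the RR denominator is the natural reading, but sections 11.2 and 11.3 do not say so.

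The upward bias is conditional on excluded patients responding less often. Its size cannot be fixed from the documents. In the worked example it is 1.7 points (29.0 − 27.3) with 2 dropped and 4.8 points (32.1 − 27.3) with 5 dropped, well inside the confidence interval. The effect on the go/no-go decision is nil without replacement. At assumed replacement rates of 2–5% under the written rule and a true RR of 23%, it is modest, though above the nominal 0.20. The sample size calculation is correct.

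**What to change.** - **Sections 6.1.1, 11.2 and 11.3:** define the primary RR denominator as all registered patients who start protocol treatment. Count anyone without a documented qualifying CR or PR as a non-responder, whatever the reason. State that a patient with a documented qualifying CR or PR who misses one scan remains a responder. Apply 3/17 and more than 9/33 to the first 17 and 33 such patients. Report the evaluable-set RR as secondary.
- **Section 5.5.3:** limit replacement for the analysis to patients who never start protocol treatment, and cross-refer to section 4.5 for continued follow-up. This concerns counting only and does not alter who stops treatment.
- **Section 6.1.2:** it allows for patients whose lesions are all treated with SABR, who therefore have no target lesions. State how they are scored for RR, so that they do not become failures by default.
- **Section 11.2:** state which denominator 23% and 36.8% refer to.

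The cost is wording, with no new procedures and no change to the 17/33 design. The reported RR may be lower. If both planning rates refer to evaluable patients, false-go/power of the 33-patient rule should be restated as 0.179/0.781, 0.155/0.742 and 0.118/0.668 at 2%, 5% and 10% non-evaluable, so power would fall below the planned 0.80.

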#### 6.1.2 Disease Parameters

Measurable disease. Measurable lesions are defined as those that can be accurately measured in at least one dimension (longest diameter to be recorded) as  $\geq$ 10 mm with spiral (Helical) CT scan. All tumor measurements must be recorded in millimeters (or decimal fractions of centimeters).

Non-measurable disease. All other lesions (or sites of disease), including small lesions (longest diameter <20 mm with conventional techniques or <10 mm using spiral CT scan), are considered non-measurable disease. Bone lesions, leptomeningeal disease (patients excluded), ascites, pleural/pericardial effusions, lymphangitis cutis/pulmonis, inflammatory breast disease, abdominal masses (not followed by CT or MRI), and cystic lesions are all non-measurable.

Target lesions. All measurable lesions up to a maximum of 3 lesions per organ and 6 lesions in total, representative of all involved organs, should be identified as **target lesions** and recorded and measured at baseline. Target lesions should be selected on the basis of their size (lesions with the longest diameter) and their suitability for accurate repeated measurements (either by imaging techniques or clinically). A sum of the longest diameter (LD) for all target lesions will be calculated and reported as the baseline sum LD. The baseline sum LD will be used as reference by which to characterize the objective tumor response.

Note: Lesions receiving SABR will be called "treated lesion" which should not be confused with "target lesions" defined here for the for the purpose of radiographic measurement. Treated lesions and target lesions are mutually exclusive lesions. Therefore, treated lesions will not be used as target lesions for evaluating response. Since patients with ANY number of metastasis is eligible for this study, in the instance where patient has only one or few site of disease and all of them are treated, appearance of new lesions (either measurable or non-measureable) will constitute PD.

Non-target lesions. All other lesions (or sites of disease) including any measurable lesions over and above the 6 target lesions should be identified as **non-target lesions** and should also be recorded at baseline. Measurements of these lesions are not required, but the presence or absence of each should be noted throughout follow-up.

## 6.1.3 Methods for Evaluation of Measurable Disease

All measurements will be done digitally on the PACs system. All baseline evaluations should be performed as closely as possible to the beginning of treatment and never more than 14 days before the beginning of the treatment.
The same method of assessment and the same technique should be used to characterize each identified and reported lesion at baseline and during follow-up using appropriate radiologic imaging.

Bone scans and CT scan of Chest, abdomen and pelvis with IV contrast will be performed at baseline. Since bone scan is not reliable for RCC, it will only be used to evaluate overall response when positive in baseline scan, and any new lesions found on bone scan must be verified with a CT.

Spiral CT and MRI. All CT scans will be Spiral CT and should be performed using a 5 mm contiguous reconstruction algorithm.

#### 6.1.4 Response Criteria

#### 6.1.4.1 Evaluation of Target Lesions

Complete Response (CR): Disappearance of all target lesions, determined by two separate observations conducted not less than 4 weeks apart. There can be no appearance of new lesions.

Partial Response (PR): At least a 30% decrease in the sum of the longest diameter (LD) of target lesions, taking as reference the baseline sum LD. There can be no appearance of new lesions.

Progressive Disease (PD): At least a 20% increase in the sum of the LD of target lesions, taking as reference the smallest sum LD recorded since the treatment started, or the appearance of one or more new lesions verified by a second scan > 6 weeks apart.

Stable Disease (SD): Neither sufficient shrinkage to qualify for PR nor sufficient increase to qualify for PD, taking as reference the smallest sum LD since the treatment started.

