## 2.0 STUDY OBJECTIVES

## 2.1 Primary Objectives

2.1.1 To evaluate the response rate (RR) in patients with mRCC after treatment with HD IL-2 immediately following SABR to multiple metastatic sites. RR has been highly correlated (p<0.0001) to overall survival [34]. RECIST 1.1 criteria will be used to measure RR and it will consist of complete response (CR) and partial response (PR).

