The SABR prescription dose will be delivered to the periphery of the planning target volume (PTV, see below for definitions). Investigators will have discretion in choosing from either of the biologically equivalent dose levels using one or three fractions, although a single fraction is preferred over three fraction treatments. Treating physician will have further discretion in selecting the number and location of sites to treat if >6 sites of disease are present. Maximum number of lesions treated is deemed as feasible per the treating radiation oncologist. Physician's will be **REQUIRED** to leave at least one site of disease for the purpose of measuring a radiographic response (see section 6.1) at a non-treated site, as this is part of the primary endpoint. If left untreated, this site can be treated once patient meets the definition of progressive disease (PD) (see section 6). To clarify the definition of "site", each site is an area or organ with active extracranial disease (</=3 in the liver = one site and </=3 in the lung= one site) identified by CT scan, or PET/CT, within 4 weeks prior to initiation of SBRT (up to 2 contiguous vertebral metastasis will be considered a single site of disease). For example: a patient with 4 right axillary lymph nodes, L1-L2 bone metastasis, 3 right lung lesions, 1 left lung lesion, 2 liver lesions, and T2-T3 bone metastasis would be defined as having 6 sites of disease. Preference should be given to the largest feasible disease site, symptomatic sites and sites where palliative and preventative (i.e. to prevent a pathologic fracture in weight bearing bone, impending cord compression, impending SVC compression etc.) indications are applicable. The gross target/tumor volume (GTV) should be at least 2cm^3 in size, corresponding to roughly a 1.5 cm diameter tumor. This is to ensure that adequate tumor volume and therefore adequate tumor cells (roughly 10^8 -10^9 cells/cm^3 [96]) are killed for antigen presentation. Treating physicians should choose their dose based on established planning guidelines at their center including their ability to respect normal tissue tolerance listed below. It is not required that all targets be treated with the same dose fractionation. A dose from the following table should be used:

	Total Cumulative Dose Encompassing 95% of Planning					
	Target Volume (Gy)					
Number of	Protocol Compliant Minor Deviation * MinorDeviation					
Fractions						

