#### 6.1.4.2 Evaluation of Non-Target Lesions

Complete Response (CR): Disappearance of all non-target lesions and normalization of tumor marker level.

Incomplete Response/Stable Disease (SD): Persistence of one or more non-target lesion(s) and/or maintenance of tumor marker level above the normal limits.

Progressive Disease (PD): Appearance of one or more new lesions and/or unequivocal progression of existing non-target lesions

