#### 6.1.4.3 Evaluation of Best Overall Response

The best overall response is the best response recorded from the start of the treatment until disease progression/recurrence (taking as reference for progressive disease the smallest measurements recorded since the treatment started). The subjects best response assignment will depend on the achievement of both measurement and confirmation criteria.

Target Lesions	Non- Target Lesions	New Lesions	Overall Response	Best Response for this Category
-------------------	---------------------------	-------------	---------------------	---------------------------------------

				Also Requires:
CR	CR	No	CR	≥4 wks. confirmation
CR	Non- CR/Non- PD	No	PR	> 4 wks. confirmation
PR	Non-PD	No	PR	
SD	Non-PD	No	SD	documented at least once ≥4 wks. from baseline
PD	Any	Yes or No	PD	
Any	PD*	Yes or No	PD	no prior SD,
Any	Any	Yes	PD	PR or CR
* In exceptional circumstances, unequivocal progression in non-target lesions may be accepted as disease progression.				

Note: Subjects with a global deterioration of health status requiring discontinuation of treatment without objective evidence of disease progression at that time should be reported as "*symptomatic deterioration*". Every effort should be made to document the objective progression even after discontinuation of treatment.

Note: If subjects respond to treatment and are able to have their disease resected, the patient's response will be assessed prior to the surgery.

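### Complete response has no lymph-node exception and depends on a tumor marker that is never defined, so some true complete responses may be recorded as partial

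*Combined protocol and SAP*

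**What the plan says.** **Objective and criteria.** The Study Summary gives the objective as "To evaluate the improvement in response rate (RR) and complete response (CR) of mRCC". Section 2.1.1 says "RECIST 1.1 criteria will be used to measure RR" and builds RR from CR and PR. Section 2.4.1 names iRECIST instead. Section 6.1 cites the RECIST publication of 2000. It then says that confirming progression or new lesions on a second scan is the sole departure from RECIST v1.1, and describes measurement by largest diameter only.

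**Target lesions (6.1.4.1).** CR is "Disappearance of all target lesions, determined by two separate observations conducted not less than 4 weeks apart", with no new lesions. PR is "At least a 30% decrease in the sum of the longest diameter (LD) of target lesions, taking as reference the baseline sum LD".

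**Non-target lesions (6.1.4.2).** CR is "Disappearance of all non-target lesions and normalization of tumor marker level". Incomplete response or stable disease (SD) is "Persistence of one or more non-target lesion(s) and/or maintenance of tumor marker level above the normal limits".

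**Overall response (6.1.4.3).** "The subjects best response assignment will depend on the achievement of both measurement and confirmation criteria". In the table, target CR with non-target CR gives CR. Target CR with non-target lesions that are neither CR nor PD gives PR.

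**Which lesions are which (6.1.2).** A lesion is measurable from 10 mm longest diameter on spiral CT, with no separate provision for nodes. A SABR-treated lesion cannot be a target lesion, and every lesion that is not a target lesion is non-target.

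**Nodes and blood tests.** Section 4.1.1 counts nodes as disease in its worked example of sites ("a patient with 4 right axillary lymph nodes"). Section 5.1.11 lists LDH, CRP and beta-2 microglobulin among the chemistries. Neither that section nor the table in 5.4 designates any test as a tumor marker.

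**The concern.** A lymph node is a normal structure, so a diseased node can respond fully and still be visible on CT. A rule that asks for disappearance by longest diameter, without a nodal provision, cannot record that outcome as CR. Separately, a condition on a marker that nobody has named cannot be applied consistently. One assessor may ignore it, another may treat it as unmet, and a third may choose a test.

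Both gaps sit on the boundary between PR and CR. That is where section 1.4 expects SABR to act, by turning partial responses into complete ones. What is at stake is the reported CR rate and the duration of CR. A CR filed as PR still counts as a response, and it stays in the duration of overall response, but it drops out of the duration of CR.

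**Working it through.** **Step 1. Trace the nodal case.** Suppose every diseased node has returned to normal size but remains visible, and everything else has gone.
- Node is a target lesion: target CR fails because the lesion has not disappeared. If the sum of diameters is down by at least 30%, the patient is PR.
- Node is non-target and all target lesions have gone: a lesion persists, so non-target status is incomplete response/SD. The 6.1.4.3 table gives PR.

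**Step 2. Trace the marker case.** Suppose all target and non-target lesions have gone.
- Non-target CR needs a marker to return to normal. No marker is designated, so this cannot be shown.
- Non-target SD needs a persisting lesion or a marker above normal. No lesion persists and no marker is designated, so this cannot be shown either.
- The patient meets neither definition. If the clause is ignored, the result is CR. If it is treated as unmet, the patient is neither non-target CR nor PD, and the table gives PR. If the assessor picks a test, the result depends on the test.

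**Step 3. Who is exposed.** Section 3.1.8 requires eligibility for SABR at one or more sites, and 6.1.1 counts a patient as evaluable for response only after SABR. Every evaluable patient therefore has a treated lesion. By 6.1.2 that lesion is not a target lesion and so falls into the non-target class. The marker clause thus bears on essentially every CR call. The same reasoning means that a residual treated lesion, read literally, could also block CR.

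**Step 4. Check the primary design.** Inputs from 11.2: null RR 0.23, target RR 0.368, stop if 3 or fewer responses in 17, succeed if more than 9 in 33.
- P(stop early at 0.23) = P(X ≤ 3), X ~ Bin(17, 0.23) = 0.427 (plan: 0.43).
- Average sample size = 17 + (1 − 0.4272) × 16 = 26.16 (plan: 26.2).
- Exact type I error 0.197 and power 0.805, both within the stated 0.20 limits.

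The plan's figures reproduce. Because RR = CR + PR, moving a patient from CR to PR leaves the response count, and so all four figures, unchanged.

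**Step 5. Size for the CR rate.** The documents do not give the share m of true CRs that would be recorded as PR. Recorded CR = true CR × (1 − m). The true rate is taken here at the 7%-9% quoted in section 1.3.

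| Assumed m | True CR 7% | True CR 9% |
|---|---|---|
| 0 | 7.0% (2.31 of 33) | 9.0% (2.97 of 33) |
| 10% | 6.3% (2.08) | 8.1% (2.67) |
| 25% | 5.3% (1.73) | 6.8% (2.23) |
| 50% | 3.5% (1.16) | 4.5% (1.48) |

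Now assume that 30-40% of complete responders have nodal disease, and that all of them keep a visible node and are downgraded. A true 9% becomes 9% × 0.7 = 6.3% to 9% × 0.6 = 5.4%. The number moved is 2.97 × 0.3 = 0.89 to 2.97 × 0.4 = 1.19, or about one patient.

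**Step 6. Compare with the precision.** Exact 95% intervals: 3/33 = 9.1% (1.9% to 24.3%); 2/33 = 6.1% (0.7% to 20.2%). One patient is a third of three CRs, but the shift is small against either interval.

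**The case against.** The strongest reply is that little depends on CR. Section 11 plans no test, sample size or decision rule for it. The 7%-9% figure is background, and the planned historical comparisons concern RR, OS and PFS. This stands, and it limits the weight of the point. CR is nevertheless named in the Study Summary and has its own duration definition in 6.1.6.

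A second reply is that 2.1.1 and 6.1 adopt RECIST 1.1 with one change only, so any nodal rule in RECIST 1.1 is already part of the plan. This stands in part. It shows that the strict rule is not settled, but the written definitions say otherwise and three criteria are named, so an assessor cannot tell which governs.

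A third reply is that 6.1 says the two randomized trials serving as historic controls used the same criteria. If they also required disappearance, the comparison would be like with like. That cannot be checked from the documents. The evaluability rule in 6.1.1 (one full IL-2 course and re-evaluation at 8 and 16 weeks) also pushes rates upward. The net direction is therefore unknown.

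A reader might go further and infer that no patient with a non-target lesion can ever be CR, or that the marker is never measured. The documents support neither. With lesions gone and no marker designated, the SD wording is not met, so the text leaves the case open and does not settle it against CR. Candidate blood tests are drawn; they are undesignated, so the marker is undefined, not unmeasured.

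**Conclusion.** The definitional gap is real. As written, CR has no provision for nodes that return to normal size, and it carries a marker condition that cannot be applied. Some true CRs may be recorded as PR. RR, the two-stage boundaries and the go/no-go decision are unaffected.

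The size is unknown. About one patient of 33 moves if the true CR rate is 9%, 30-40% of complete responders have nodal disease, and all of these are downgraded; none of those shares comes from the documents. The marker clause could reach more patients, depending on how assessors handle it.

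It is tempting to conclude that the trial will understate CR relative to the historical 7%-9%. The documents do not support that, because the misfiling is conditional, the historical rule may be the same, and evaluability works the other way. The point merits correction because the wording governs a stated objective and is cheap to repair.

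**What to change.** 1. Delete the tumor-marker condition from both the CR and the SD lines of 6.1.4.2.
2. Reconcile 2.1.1, 2.4.1 and 6.1 to one governing response criterion. In 6.1.4.1 and 6.1.4.2, state that a lymph node that has returned to normal size under that criterion's nodal rule counts as resolved for CR.
3. State in 6.1.2 or 6.1.4 whether a residual SABR-treated lesion counts against CR.
4. Report CR under the strict disappearance rule as a sensitivity analysis.

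The cost is protocol wording and, if the chosen nodal rule needs it, one more measurement field on scans already scheduled. No change to sample size or boundaries is needed. The drawback is that CR may become less comparable with historical trials that required strict disappearance; item 4 addresses this.
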